Hypothesis I-a: C-tDCS will be safe in AIS patients receiving EVT with no increased risk of symptomatic intracranial hemorrhage (SICH) within the 24-hour period after EVT. Hypothesis I-b: C-tDCS will not increase the rates of asymptomatic intracranial hemorrhage, early neurological deterioration (NIHSS during the 24-hour period after stimulation), 90-day mortality, and all serious adverse events. Hypothesis I-c: Majority of AIS patients ($\geq 90\%$) will tolerate the C-tDCS by completing at least 75% of the stimulation period with no major stimulation related pain, discomfort and skin changes.

Specific Aim II: To determine the feasibility of delivering C-tDCS as an adjunct and bridge to EVT.

Hypothesis II-a: Adjunctive C-tDCS after endovascular thrombectomy will be started more rapidly after the end of ET procedure over the course of the study and in the last 10 patients, median time from end of ET procedure to C-tDCS initiation will be ≤ 10 minutes. Hypothesis II-b: Bridging C-tDCS prior to endovascular thrombectomy will be started more rapidly over the course of the study and in the last 4 patients, median time from randomization to C-tDCS initiation will be ≤ 10 minutes.

Specific Aim III: To explore the potential imaging and clinical efficacy of tDCS in AIS as an adjunct and bridge to EVT.

1) Early and late penumbral salvage, defined as proportion of penumbral tissue on baseline multimodal MRI that does not proceed to infarct on 2-hour and 24-hour MRI (PWI); 2) Early and late collateral enhancement, evidenced by reduced perfusion lesion volume on 2-hour and 24-hour perfusion-weighted MRI (PWI); 3) Early and late reduction in infarct growth from baseline to 2-hour and 24-hour MRI; 4) Early improvement in neurologic deficit (NIHSS at 24h); 5) Improvement in final 3-month disability and quality of life (modified Rankin scale, AMC Linear Disability Scale, EQ-5D, and Barthel Index)

Impact

This in-hospital safety trial, will identify C-tDCS dose regimens that are feasible, well-tolerated, and preliminarily safe in patients with acute ischemic stroke who undergo ET. Study finding will identify the most promising dose regimens to advance to phase 2b and pivotal phase 3 efficacy trials for three patient populations with pressing need for improved therapies: 1) thrombectomy-eligible patients arriving directly to thrombectomy-capable hospitals who would benefit from post-arrival brain protection; 2) thrombectomy-eligible patients arriving initially

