Emergent multimodal MR and CT is currently acquired as the routine initial imaging study in all acute stroke patients at UCLA. In patients receiving MRI, a 1.5 T or 3 T scanner equipped with echo-planar imaging capability is used for rapid acquisition of diffusion and perfusion scans. The standard clinical MRI protocol includes Gradient Recall- Echo (GRE), DWI, FLAIR (Fluid-Attenuated Recovery Image), PWI and MR angiography. The ADC (apparent -diffusion coefficient) values derived from DWI acquisition ($b=0, 1000 \text{ s/mm}^2$ applied in each of three principal gradient directions) will be used to delineate the volume of ischemic core. The tissue with ADC values of $\leq 620 \mu\text{m}^2/\text{s}$ will be considered ischemic core, indicative of tissue with advanced, irreversible bioenergetic compromise. FLAIR delineates early parenchymal signal abnormality associated with ischemia and slow retrograde flow in leptomeningeal collaterals appearing as FLAIR vascular hyperintensity (FVH). The GRE sequence is used to evaluate the presence of intracranial hemorrhage and deoxygenated leptomeningeal collaterals appearing as GRE vascular hypointensity (GVH). PWI is acquired with sequential T2*-weighted (gradient echo) EPI time sequence scanning. Early in the time series, a bolus (0.1 mmol/kg) of MRI contrast material is rapidly infused (5 ml/sec through an 18 or larger gauge angiocatheter) using a power injector. The perfusion lesion volume (tissue at risk volume) will be the region with $\text{Tmax} \geq 6\text{sec}$ ($\text{Tmax} = \text{the time delay from}$

the arrival of contrast to its peak concentration at the tissue vasculature). ^{43,44} Intracranial CEMRA (Contrast-Enhanced MRA) will identify large vessel occlusion.

In patients receiving CT, the standard clinical CT protocol includes non-contrast CT (NCCT), multiphase CT angiography, CT perfusion (CTP) processed through RAPID software. NCCT is used to rule out acute intracranial hemorrhage appearing as hyperdensity. The tissue with rCBF < 30% on CTP will be considered ischemic core and the perfusion lesion volume (tissue at risk volume) will be the region with Tmax ≥ 6sec. CT angiography (CTA) will identify large vessel occlusion.

- Endovascular Thrombectomy

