Follow-up MR/CT multimodal imaging will be obtained routinely at UCLA at 2h and 24h post-thrombectomy (supported by Radiology Dept. research funds). MRI Imaging sequences will include DWI/FLAIR/GRE/PWI/CEMRA and CT imaging sequences will consist of NCCT/CTA/CTP. RAPID image processing software will be applied to the above images to quantify, at the baseline, 2h, and 24h time-points: 1) Early penumbra preservation: Volume of baseline penumbra tissue not progressing to ischemic core at 2h; 2) Penumbra salvage: Volume of baseline penumbra tissue not progressing to ischemic core at 24h; 3) Early collateral flow enhancement: Perfusion lesion volume at baseline – Perfusion lesion volume at 2h; 4) Sustained collateral flow enhancement: Perfusion lesion volume at baseline – Perfusion lesion volume at 24h; 5) Early infarct growth: Ischemic core lesion volume at 2h – Ischemic core lesion volume at baseline; and 6) Final infarct growth: Ischemic core lesion volume at 24h – Ischemic core lesion volume at baseline. Additional location and extent of ischemic injury at baseline, 2h, and 24h will be rated using the ASPECTS scoring system.

D.6.10. Adverse Events

D.6.10.1 Serious Adverse Events (SAEs)

All serious adverse events occurring during the 90 days of study participation will be recorded. A serious adverse event is any adverse event that is fatal, is life-threatening, is permanently or substantially disabling, requires or prolongs hospitalization, or requires medical or surgical intervention to prevent one of the above outcomes.¹⁸

D.6.10.2 Symptomatic intracranial hemorrhage

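### The plan's only CT definition of ischemic core is a flow threshold, and no other CT rule is given for 2h and 24h after thrombectomy; carried forward, it misses infarct that has reperfused

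*Combined protocol and SAP*

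**What the plan says.** Section D.6.9 (Imaging Assessments) defines ischemic core separately by modality, under its Baseline bullet.

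- **CT:** "The tissue with rCBF < 30% on CTP will be considered ischemic core". Non-contrast CT has one stated role: "NCCT is used to rule out acute intracranial hemorrhage appearing as hyperdensity".
- **MRI:** tissue at or below an ADC of 620 µm²/s "will be considered ischemic core, indicative of tissue with advanced, irreversible bioenergetic compromise".

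The part of D.6.9 on follow-up opens with "Follow-up MR/CT multimodal imaging will be obtained routinely at UCLA at 2h and 24h post-thrombectomy". For CT, it says that "CT imaging sequences will consist of NCCT/CTA/CTP". It then states that "RAPID image processing software will be applied to the above images to quantify, at the baseline, 2h, and 24h time-points" six endpoints. Four of these depend on core at follow-up: early and late penumbral salvage, and early and late infarct growth. The last, for example, begins "Final infarct growth: Ischemic core lesion volume at 24h" and subtracts baseline core. This part contains no CT definition of core or infarct of its own. ASPECTS is rated as an addition and does not enter the volumes.

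Aim III (section A) words the growth endpoint differently: "Early and late reduction in infarct growth from baseline to 2-hour and 24-hour MRI". It also places penumbral salvage on MRI. The adjunctive-stimulation management section (D.4), the schedule in D.6.1 and section D.6.9 all allow MRI or CT.

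E.3.5.2 summarises the imaging endpoints by arm and by dose tier with means and confidence intervals. It does not mention modality.

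**The concern.** Between the baseline scan and the follow-up scans the patient has a thrombectomy, whose purpose is to restore flow. A low-flow threshold can stand in for core while the vessel is blocked. Once flow has returned, infarcted tissue no longer meets the threshold and drops out of the measured core.

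The four core-dependent endpoints then partly measure reperfusion, which the two collateral-flow endpoints already address. ADC-based MRI values are on a different footing, so a pooled mean depends on which scanner each patient happened to have.

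Two features raise the stakes. Section C.3 argues that tDCS may itself increase blood flow, so the error could differ by arm and resemble benefit. And D.6.10.2 says that the decision on further development will weigh all the outcome measures, so the exploratory endpoints are not idle.

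**Working it through.** **Reproducing the plan's own figure.** E.2.1 gives 24 to 48 patients: 6 tiers × (3 + 1) = 24 and 6 × (6 + 2) = 48. This agrees. The imaging endpoints carry no stated size, SD or effect.

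**Who can have restored flow at follow-up.** Adjunct stimulation requires a TICI grade below 2c (D.3.1). That includes 2b, which D.6.9 defines as 51-90% of the territory reperfused, but also grades 0 to 2a. Patients in tiers 5 and 6 are enrolled before thrombectomy and can end at 2c or 3.

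**Formulas.** These apply the D.6.9 endpoint definitions. Let C0 be baseline core, P baseline penumbra, F true infarct at follow-up, and r the share of infarcted tissue whose flow is back above the rCBF threshold, taken as equal in old and new infarct.

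- Recorded core = F(1 − r)
- Recorded growth = F(1 − r) − C0
- Recorded salvage, as a share of P = 1 − (F − C0)(1 − r)/P

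**Assumed inputs (the documents give no volumes).** C0 = 40 mL, P = 60 mL, F = 60 mL. True growth is 60 − 40 = +20 mL. True salvage is 1 − 20/60 = 67%.

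| r | Recorded core (mL) | Recorded growth (mL) | Recorded salvage |
|---|---|---|---|
| 0 | 60 | +20 | 67% |
| 0.25 | 45 | +5 | 75% |
| 0.51 | 29.4 | −10.6 | 84% |
| 0.90 | 6 | −34 | 97% |

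Recorded growth reaches zero at r = 1 − C0/F = 1 − 40/60 = 0.33 and is negative beyond that.

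**Which tissue causes which error.** At r = 0.51 the growth error is −60 × 0.51 = −30.6 mL. Of this, 40 × 0.51 = 20.4 mL is baseline core that has reperfused and 20 × 0.51 = 10.2 mL is penumbra that infarcted and then reperfused. Only the second part enters salvage, because salvage counts baseline penumbra alone.

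**Effect on an arm mean.** The penumbral substudy in D.3.1 is limited to the bridging tiers. If tiers 5 and 6 are both completed, they hold 2 × 1 = 2 to 2 × 2 = 4 sham patients. One such CT patient shifts the sham mean growth by −30.6/2 = −15.3 mL or −30.6/4 = −7.7 mL. The same patient among 6 to 12 active patients shifts that mean by −30.6/6 = −5.1 mL or −30.6/12 = −2.6 mL.

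**The case against.** **The rCBF sentence stands under Baseline.** The follow-up part of D.6.9 never mentions rCBF, and the images it sends to the software include non-contrast CT, DWI and FLAIR as well as CTP. This stands as a limit: use of the threshold at 2h and 24h is inferred. A reader might conclude that the plan expressly prescribes rCBF at follow-up, and the text does not go that far. But the term, the CT perfusion sequence and the software are the same, non-contrast CT has no infarct-volume role, and no alternative is given.

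**Aim III may exclude CT altogether.** On its wording, no CT value would enter these endpoints. That would remove the bias, but it conflicts with the sections that allow MRI or CT, and the plan does not say which governs.

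**Reperfused tissue is not all counted as salvaged.** A reader might infer that any infarct with restored flow is scored as saved. That is too broad: reperfused baseline core distorts growth only.

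**TICI grade does not give the size of the error.** It is tempting to read the 51-90% for grade 2b as the share of infarct that drops out. TICI is an angiographic share of a territory, not the share of infarcted voxels above an rCBF threshold, and the core may lie mainly where flow did not return. With no restored flow the error is nil. The documents also do not say how many patients will have CT.

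**The endpoints are exploratory.** E.3.5.2 says so, and escalation rests on SICH and the DSMB's safety review. This limits the consequence, but exploratory status excuses imprecision rather than an error with a known direction.

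**Conclusion.** The concern holds as a gap whose natural reading produces a biased measure. For CT patients, the only core definition in the plan depends on flow, and nothing replaces it after thrombectomy. Carried forward, it biases infarct growth down in patients whose flow has returned, and biases salvage up where penumbra infarcts and then reperfuses. Pooling with ADC-based values mixes two definitions, and the modality conflict between Aim III and D.6.9 is in the text however the first point is read.

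The direction is supported; the size is not. The −10.6 mL against +20 mL, and the 84% against 67%, rest on assumed volumes and an assumed share of 51%. The shift of −15.3 to −7.7 mL in a sham mean further assumes that tiers 5 and 6 are both completed and that all 2 to 4 of their sham patients enter the imaging analysis.

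A reader might also infer that the results will favour tDCS. The documents support only the possibility: section C.3 expects an effect on flow, but the plan gives no figure for it, and a CT patient in the sham arm would push the comparison the other way. The SICH endpoint and the escalation rule are not affected. The change is worth making before images are read, but it does not bear on whether the trial can proceed.

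**What to change.** In D.6.9 and E.3.5.2:

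- State that rCBF < 30% defines baseline core only.
- Define 24h infarct by tissue: DWI/ADC or FLAIR on MRI, and hypodensity on the non-contrast CT already in the follow-up set.
- At 2h, do not use CTP core as infarct. Report 2h CT growth and salvage separately or as not assessable. Do not pool them, and exempt them from the multiple imputation that E.2.1 prescribes for missing data.
- Report imaging results by modality and arm.
- Reconcile Aim III with D.6.9 on whether CT counts for these endpoints.

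The cost is wording in the protocol, the analysis plan and the imaging reading rules; no new scans are needed. There are two real downsides. Some 2h CT values are lost from a small subgroup, and some modality-by-arm cells may be empty. For CT patients, the baseline measure (flow) and the 24h measure (tissue) will differ in type, so their growth values should be read with that stated.

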After randomization and during the stimulation, all patients will be monitored closely by a physician-investigator. NIHSS will be obtained at the end of each 20-minute stimulation cycle and a visual inspection of the skin and rate degree of any potential erythema under the electrode will be performed. Then, a tolerability form will be completed based on validated cutaneous, neurological, and pain items of the PRO-CTAE (Patient-Reported Outcomes version of the Common Terminology Criteria for Adverse Events) (Figure 8).^{40,41}

After the stimulation, nursing neurologic assessments will be performed by Neurointensive Care Unit with extensive experience in monitoring acute stroke patients. Specifically, patients will be monitored for any signs of neurological worsening and will be queried on development of new or worsening neurological symptoms, including headache, dizziness, numbness, or weakness, etc. If any sign or symptom of neurological worsening is suspected, the patient will be immediately assessed by the on-call neurologist and an immediate brain imaging (CT or MRI) will be obtained. Neuro-checks will be performed at 1h and 2h after stimulation and then every 2 hours. Subsequent care will be continued in these settings, including medical management per national guidelines for acute ischemic stroke management issued by the American Stroke Association.⁴² Patients will not receive NSAIDs as concomitant therapy for the first 7 days after enrollment. All patients will undergo a multimodal MRI or CT including standard parenchymal images, non-invasive angiography, and perfusion studies and formal NIHSS assessment at 2-hour and 24-hour following the end of the stimulation tier as part of the study protocol.

D.5. Management pre, during, and post bridging stimulation

At tiers 5 and 6, hospital arriving patients who are candidates for EVT with an LVO detected on CT angiography and are being transferred to agio suite for EVT procedure will receive up-to-20 minutes of stimulation. See section D.4. for care during and post-stimulation.

Figure7: Technician-filled tolerability form	Presence		Severity		Effect on the study treatment (Shortened the stim duration)		Duration/Frequency			Treatment			
	A	P	M	Mod	S	Y	N	< 50 % of stim period	≥50% of stim period	lasted after stim period (min)	None	Con	Med
Adverse Events													
Rash													
Skin dryness													
Hair loss													
Itching													
Hives													

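### Infarct growth and penumbral salvage may compare a CT blood-flow core with an MRI diffusion core, and all such pairs are pooled into one mean per arm

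*Combined protocol and SAP*

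**What the plan says.** **Core definitions (D.6.9, Baseline).** On MRI, tissue with ADC ≤ 620 µm²/s "will be considered ischemic core, indicative of tissue with advanced, irreversible bioenergetic compromise". On CT, "The tissue with rCBF < 30% on CTP will be considered ischemic core". The perfusion lesion is Tmax ≥ 6 sec on both.

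**Modality at baseline.** D.6.9 opens with "Emergent multimodal MR and CT is currently acquired as the routine initial imaging study in all acute stroke patients at UCLA" and then sets out one path for patients who receive MRI and another for those who receive CT. For patients arriving at the hospital in Tiers 5 and 6, D.5 speaks of candidates "with an LVO detected on CT angiography".

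**Modality at follow-up.** The management section D.4 says "All patients will undergo a multimodal MRI or CT including standard parenchymal images, non-invasive angiography, and perfusion studies" at 2 and 24 hours. The schedule in D.6.1 has a single row for either modality at baseline, 2 hours and 24 hours, and the follow-up part of D.6.9 also allows MR or CT.

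**Endpoints (D.6.9, follow-up part).** "Early infarct growth: Ischemic core lesion volume at 2h – Ischemic core lesion volume at baseline"; final growth is "Ischemic core lesion volume at 24h – Ischemic core lesion volume at baseline". Penumbral salvage is the baseline penumbra that has not become ischemic core by follow-up.

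**Aim III.** Penumbral salvage is the "proportion of penumbral tissue on baseline multimodal MRI that does not proceed to infarct on 2-hour and 24-hour MRI (PWI"). For infarct growth and collateral enhancement, Aim III names MRI at 2 and 24 hours and no modality at baseline.

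**Analysis (E.3.5.2).** Means and 95% CIs by active and sham and by higher and lower dose tiers. Modality is not mentioned.

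**The concern.** A diffusion threshold and a blood-flow threshold measure different tissue properties. If one gives the baseline volume and the other the follow-up volume, their difference is true change plus the gap between two instruments. Nothing in the plan prevents that pair, labels it, or keeps it apart from like-with-like pairs.

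The pair is plausible where it matters. The imaging analysis centres on the bridging tiers, for which D.5 names CT angiography, while Aim III names MRI at follow-up. A patient imaged by CT at baseline and then scanned as Aim III describes produces exactly this mixture.

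What is at stake is the reading of the Aim III imaging signals. D.6.10.2 says the decision on further development will weigh all outcome measures, so a summary labelled infarct growth should measure infarct growth.

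**Working it through.** **1. The plan's own sample size.** E.2.1 gives 24 to 48. Six tiers × (3 active + 1 sham) = 24; six tiers × (6 + 2) = 48. Both reproduce.

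**2. Size of the imaging subset.** The substudy criteria in D.3.1 limit it to tiers with a bridging session, which are Tiers 5 and 6. Two tiers give 2 × 3 = 6 active and 2 × 1 = 2 sham. If both expand, they give 12 active and 4 sham. The penumbra ratio of at least 1.2 can only reduce these counts.

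**3. What a mixed pair measures.** Let M and C be the core volume on MRI and CT, with subscripts for time in hours. For a CT baseline and an MRI follow-up:

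M₂₄ − C₀ = (M₂₄ − M₀) + (M₀ − C₀)

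The first bracket is growth on the MRI definition. The second is the offset b, which is not growth. The reverse switch gives C₂₄ − M₀ = (M₂₄ − M₀) + (C₂₄ − M₂₄), with the offset now arising at follow-up. Salvage is affected less directly, because the follow-up core decides which part of the baseline penumbra counts as lost.

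**4. Shift in an arm mean.** One mixed pair among n patients moves the mean by b/n. The documents give no b, so 5, 10 and 20 ml are assumptions:

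| Arm | n | b = 5 | b = 10 | b = 20 |
|---|---|---|---|---|
| Sham | 2 | 2.5 | 5 | 10 |
| Sham, both tiers expanded | 4 | 1.25 | 2.5 | 5 |
| Active | 6 | 0.8 | 1.7 | 3.3 |
| Active, both tiers expanded | 12 | 0.4 | 0.8 | 1.7 |

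(Shift in ml.)

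**5. Would randomisation balance it?** Assume each patient independently has a mixed pair with probability 25%, 50% or 75%, the same in both arms. Exact binomial enumeration gives the chance that the mixed share differs between arms: 84% to 85% at 6 versus 2, and 87% to 89% at 12 versus 4. The expected absolute difference in share is 0.287 to 0.328 and 0.200 to 0.232 respectively. Multiplying by b = 5 to 20 ml gives an expected spurious difference of 1.4 to 6.6 ml (0.287 × 5 to 0.328 × 20) and 1.0 to 4.6 ml (0.200 × 5 to 0.232 × 20).

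**6. Against the planned intervals.** The half-width of a t-based 95% CI for a sham mean is 8.98 SD at n = 2 and 1.59 SD at n = 4. With an assumed SD of 10 to 30 ml, that is about 90 to 270 ml and 16 to 48 ml. The shifts in step 4 lie inside these.

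**The case against.** The strongest reply is that the endpoints carry no weight that an offset could upset. E.3.5.2 calls them exploratory and descriptive, with no test or threshold, and step 6 shows that sampling noise is far larger than the assumed shifts. That stands as a limit on importance. It does not make the label correct: wide intervals express patient-to-patient variation, and they do not tell the reader that some values are differences between unlike measurements.

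A second reply is that mixing is inferred from silence, since D.6.9 describes MRI patients and CT patients separately and plans no switch. It is true that no switch is planned and no rate is given. But those paths describe baseline imaging, follow-up is left open, and Aim III's follow-up MRI invites a switch for anyone with a CT baseline. If D.6.9 meant that every patient has both modalities at baseline, the plan would still not say which volume enters the subtraction.

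Several stronger readings are tempting, and the documents do not support them:

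- *All six imaging endpoints are affected.* Early and sustained collateral enhancement use Tmax ≥ 6 sec on both scanners, so the two-definition problem does not reach them.
- *Aim III puts every imaging endpoint on MRI at all three times.* It names baseline MRI only for penumbral salvage.
- *The artefact favours one arm.* Nothing shows a direction; under randomisation it is chance imbalance.
- *Every patient should be rescanned on the baseline modality, or only matched pairs analysed.* Neither is clearly better. CT follow-up would conflict with Aim III, and a flow-based core can shrink after thrombectomy because flow is restored. Dropping mixed pairs could empty a sham arm of 2 to 4.

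**Conclusion.** The point holds for early and final infarct growth directly and for penumbral salvage indirectly. For these, the plan allows a CT core to be compared with an MRI core, in either order, and pools every pair into one mean per arm. Aim III and the sections that allow MRI or CT do not agree and must be reconciled.

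The size follows from the design only as a fraction: one mixed pair moves the sham mean by half the offset with 2 sham patients, or a quarter with 4. Every figure in ml rests on assumed offsets, and the imbalance figures also on assumed switching rates. The sham counts rest on reading the imaging subset as Tiers 5 and 6. E.3.5.2 is loosely worded, but a count of 6 sham patients would need all six tiers and does not fit the substudy criteria.

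This is a matter of how exploratory imaging results are read. The primary safety result and dose escalation are unaffected.

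**What to change.** 1. Reconcile Aim III with D.4 (adjunctive-stimulation management), D.6.1 and D.6.9, so that one modality rule for the study imaging endpoints is stated in advance, including which volume is used if a patient has both scans at one time.
2. In E.3.5.2, report early and final infarct growth and penumbral salvage by modality pair (MRI-MRI, CT-CT, mixed) instead of pooling them. Show mixed pairs separately and do not discard them.
3. Tabulate modality by arm and time point.
4. Add a note that CT-CT core differences after thrombectomy may reflect restored flow.

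The cost is a few sentences and one table. The downside is smaller cells in a summary that is already descriptive: with 2 to 4 sham patients, some modality-pair cells will hold one patient or none and are best shown as individual values.
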